5.4 Blinding

The study drug and placebo will be manufactured by an external facility and supplied to each site pharmacy in pre-prepared and coded bottles. Each bottle will be numbered according to the pre-determined allocation code and labeled as:

Study number 035/16 Melatonin prolonged release (2mg)/ placebo. Take one tablet every night at 2000 hours after food during admission.

Treatment allocation will not be disclosed to study staff, treating clinicians or investigators. The code will only be broken in cases of extreme emergency. Such situations only include where knowledge of the code will have consequences for clinical decision making in consultation with the Lead Chief Investigator.

5.5 Method of administration

The pharmacists at the study sites will dispense the study medication. All medications must be dispensed in accordance with the delivery system used within the study site.

The intervention will be delivered at 2000 hours (± 1 hour). At each dose, the individually labeled bottle will be opened and the prescribed dose taken out. The clinical nurse will observe the participant while the participant swallows the tablet whole, and then record the administration in the medicine record.

5.6 Drug accountability

All active medicine must be stored in a locked medicine cabinet at or below 25°C within the site pharmacy. The pharmacy will maintain accountability records, in addition to the study allocation records. On dispensing to the inpatient unit, the medicine will be stored within a locked medicine cabinet appropriate to state regulations. The medicine will be checked and recorded by an appropriately qualified nurse on administration to the patient.

5.7 Drug supply

The medicine will be supplied in the following manner;

- 1. Oral melatonin 2mg prolonged release (Neurim Pharmaceuticals Ltd)
- 2. Oral placebo tablet containing identical ingredients except the active ingredient melatonin (amino methacrylate co-polymer, lactose, silicon dioxide, talcum and magnesium stearate) to ensure matching taste, size, shape and colour.

5.8 Drug destruction

All unused study drug will be destroyed on completion of the study. Unused and empty bottles in the inpatient unit will be delivered back to the pharmacy, using the established practice within the hospital.

All unused bottles returned to pharmacy will be destroyed in a manner consistent with the applicable regulations governing destruction in each state. The pharmacy Standard Operating Procedures and state regulations are to be referred to and adhered to at all times.

5.9 Concurrent treatments

Trial patients are to continue their current medicine regimen. Any changes in concomitant medications must be documented in the Case Report Form.

Benzodiazepine and antipsychotic as concurrent treatments: regular use and administration of 'as required' doses of all benzodiazepine and antipsychotics will be recorded daily, including the clinical indication. This will capture whether there is a reduced need for nocturnal sedation due to concurrent melatonin use and benzodiazepines/antipsychotic administration for delirium symptoms.

5.9.1 Non-pharmacological strategies for delirium risk

Components of inpatient care that may influence delirium risk will be standardised across centres via an evidence – based non-pharmacological protocol in domains of sleep preservation, mobility, orientation and sensory deficit minimisation, for which study staff will receive training.

This will include assessment of the patient's readiness for mobility and exercise, and to encourage and coordinate passive or active range of motion exercises, sitting out of bed and/or ambulation as appropriate. The study staff will also ensure that participants who need hearing aids and glasses have them to use, sleep preservation techniques are followed where feasible for the individual participant (noise reduction, normal day night illumination, promoting comfort and relaxation), and provide reorientation conveying day, date, place and reason for hospitalisation, and having clock and calendar visible. ⁵⁶

5.10 Rescue medications

There are no specific rescue medications, however as required benzodiazepines and antipsychotics will be recorded.

5.11 Dose modification

There are no dose modifications of the study medication allowed.

5.12 Cessation of study drug

- Participant request
- Unacceptable side effects from study medications (defined by National Cancer Institute Common Criteria for Adverse Events; CTCAE version 4.0).
- Participants who in the opinion of the investigator are not well enough to continue the study (Specific reasons for withdrawal need to be documented in the Case Report Form)
- Treatment deemed ineffective by treating clinician, who wishes to use alternative therapy.
- Occurrence of delirium (completion of study)
- Can no longer swallow
- Discharge from Hospital (completion of study)
- The participant withdraws their consent, with or without consent to use already collected data.
- It is inappropriate to continue the study medication for whatever reason

5.13 Post study treatments

All participants will be followed by their clinician for continuing care, irrespective of the point at which they exit the study.

Treatment continuation: Melatonin will only be available for currently approved indications (primary insomnia) if the participants meets that indication, after study completion (on discharge). The treatment available to reduce delirium risk after discharge will be determined by the treating clinician, and can include individualised strategies to reduce risk of delirium including regular exercise as tolerated, maintaining vision and hearing or using aids, regular reorientation and non-medication methods to improve sleep (quiet room, relaxation for example).

In all study participants, regardless of above choices, secondary outcomes and collection of data for will occur until the end of the inpatient admission after randomization, unless consent is withdrawn

5.14 Follow-up

During the follow-up phase frequency of adverse events, delirium (based on medical record), quality of life, medication and health service usage will be measured up to death or 21 days after ceasing study medication (whichever is the shorter period). These data will be collected via a weekly telephone call to the participant if they have been discharged home. Carer experience will also be captured using the Carer Experience Scale.

We will record the date of death for all participants where possible, including post recruitment. The census date will be 28 days after recruitment of the last participant to the study.

Economic evaluation

Limited evidence suggests that interventions to prevent delirium or reduce its duration in hospital are cost effective, ^{57,58} with the majority of cost offsets from longer term care savings. ⁵⁷ Estimating cost offsets over shorter time frames is crucial given advanced cancer has limited prognosis, and in prior cost-effectiveness studies, patients with terminal illness were excluded. ³⁴ The cost-effectiveness sub-study will evaluate the within-study incremental resource use, cost and consequences of melatonin relative to placebo for preventing delirium in advanced cancer patients from randomisation to study end or death (whichever is sooner). The analysis will include efficacy (delirium-free days), toxicity, survival and resource data (intervention costs, hospital length of stay, health professional time, medication use and investigations). Sampling and parameter uncertainty will be estimated by bootstrapping on participants' costs and effect pairs to maintain covariance in re-sampling with replacement across 10,000 replicates. Cost-effectiveness acceptability curves, sensitivity and scenario analyses will be undertaken.

6.0 OUTCOMES AND MEASURES

6.1 Primary outcome and measure

Delirium-free days (which occur before delirium onset for any participant who develops delirium).

6.2 Secondary outcomes

The secondary endpoints provide a profile of delirium risk and precipitants, measure toxicities, inform the health economic analysis; and explore the collateral benefits in sleep. The severity and duration of delirium, and its impacts will be evaluated if it occurs. Days in coma will also be measured as this may occur in severe irreversible delirium prior to death. Sleep quality will require participant involvement, measured every five days only to minimize participant burden.

Delirium profile: DRS-R-98 cut off score ≥17.75 will diagnose delirium and as a continuous variable will assess severity.

Toxicity: Sedation will be rated daily by observation using the Richmond Agitation-Sedation Scale - Palliative (RASS - Pal). This has modified the intensity of verbal or physical stimuli required to avoid additional discomfort in the palliative population, and has good correlation with the original RASS (interclass correlation coefficient 0.83 – 0.98). It is 10-point scale using observation, verbal stimulation, and physical stimulation, differentiating between different potency of stimulation (verbal versus physical), and also examines constructs related to delirium (agitation, sedation, inattention as measured by eye contact). It will also assess days in coma defined as RASS-Pal score of -4 or -5. Other adverse effects will be assessed using the National Cancer Institute Common Terminology Criteria.

Benzodiazepine and antipsychotic use: regular use and administration of 'as required' doses of all benzodiazepine and antipsychotics will be recorded daily, including the clinical indication. This will capture whether there is a reduced need for nocturnal sedation due to concurrent melatonin use and benzodiazepines/antipsychotic administration for delirium symptoms.

Delirium risk factors: will be recorded at baseline: age (>65 and >80 years of interest), cognitive impairment defined as SBT score >4, visual impairment, presence of infection, and use of physical restraint. Risk factors which have uncertain/contradictory evidence will also be collected to advance the science for future work: primary or secondary brain malignancy, benzodiazepines (oral diazepam equivalents), corticosteroids (oral dexamethasone equivalents), opioids (oral morphine equivalents), hearing impairment, comorbidities (Charlson Comorbidity Index), diagnosis of depression, use of indwelling bladder catheter, number of room/bed changes during admission, multiple medications (number of medications), and high blood urea/creatinine ratio (>18).

Delirium precipitating factors: The Delirium Etiology Checklist (DEC) will be completed at time of delirium occurrence. The DEC is a structured tool that utilizes clinical information from all sources, and then applies a weighted approach to each category of potential delirium precipitants.³ Each category is rated as ruled out (0), present and apparently not contributory (1), present and possibly contributory (2), likely cause (3), or definite cause (4). It can document multiple concurrent causes.

In-hospital complications: Falls, pneumonia, thromboembolism, pressure areas, changes in performance status (AKPS⁶¹) and survival will be documented, complications which increase if delirium occurs.

Family distress (Delirium experience questionnaire): The Delirium Experience Questionnaire is a face-valid, brief instrument that assesses recall of the delirium experience and distress related to the delirium episode in patients, spouses/caregivers, and nurses, and has been used in cancer patients.²⁴

Sleep quality: will be measured using the Insomnia Severity Index at baseline and every 5 days during the admission, which has established psychometric properties in cancer. The ISI is a 7-item scale that characterizes the type of sleep problem (difficulty falling asleep, staying asleep or waking up too early), and assesses impact (sleep satisfaction, associated distress and impact on others).

Inpatient resource utilisation: variables include duration of admission (days), daily medications, investigations (blood tests, imaging, urine cultures), and level of nursing required for transfers or care (independent, standby assistance, one or two assistants) and use of one to one nursing (hours).

7.0 STUDY ASSESSMENTS

7.1 Laboratory measures

Liver function tests, serum electrolytes, INR (for participants on warfarin only) and full blood count will be taken to ensure eligibility is met and at delirium occurrence to assess contributing factors to the aetiology of the delirium episode.

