- 5. provide other symptom benefits in the form of improved sleep quality.

Treatment schedule: Oral melatonin prolonged release (2mg) or placebo taken at 2000 hours. Intervention will be commenced within 48 hours of admission and continued until delirium occurrence, discharge or three weeks if patient remains in hospital (e.g. while awaiting long-term care placement) after any acute medical issues imparting a delirium risk have been resolved.

Assessments: Delirium Rating Scale – Revised – 98 (DRS-R-98);¹ Nursing Delirium Screening Scale (NuDESC);² Delirium Etiology Checklist (DEC);³ Short Blessed Test (SBT);⁴ Insomnia Severity Index (ISI); ⁵ Charlson Comorbidity Index;⁶ Richmond Agitation-Sedation Scale (RASS);⁷; EQ-5D-5L⁸, Australian Karnofsky Performance Status (AKPS);⁹ 15ml blood will be drawn at baseline and any delirium events.

Definition of response: no delirium defined as DR-R-98 ¹ (total score <17.75) for entire admission.

Primary endpoint: Delirium-free days (which occur before delirium onset for any participant who develops delirium).

Analysis: Intention-to-treat analysis will be used for all statistical comparisons. For the primary outcome, comparisons between groups for delirium-free days, with adjustment to the length of stay and other potential covariates using a general linear model approach will be undertaken. For the secondary outcomes, time-to-event analysis, such as survival analysis will be used to determine differences in time to first episode of delirium. Delirium precipitants, which occur at variable times and for different durations during the study period are time-dependent covariates and proportional logistic regression modelling will be used. The incidence rate of delirium, will also be calculated and compared between the treatment and control groups. Two planned interim analyses will be conducted independently and reviewed by the independent data and safety monitoring committee after about 33% and 66% of patients have been enrolled. The primary outcome and adverse events will be compared between groups with p<0.001 required as the threshold of stopping the trial for significant evidence of benefit or harm in either one of the treatment arms.

Economic analysis:

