The delirium etiology checklist (DEC) will be completed at time of incident delirium, in conjunction with the participants treating physician. The DEC is a structured tool that utilizes clinical information from all sources, and then applies a weighted approach to each category of potential delirium precipitants.³ Each category is rated by treating physician as ruled out (0), present and apparently not contributory (1), present and possibly contributory (2), likely cause (3), and definite cause (4). It can document multiple concurrent causes of delirium, which is important in cancer patients where the average number of precipitants is 3 or more.¹⁵ This checklist will also be completed during the study period if new precipitants are identified. Day of resolution of prior precipitant will also be recorded. If a new potential precipitating factor occurs after day 7 of the study period the DRS-R-98 will be readministered.

7.8.4 Sleep quality:

Sleep quality will be measured using the Insomnia Severity Index (ISI) at every 5 days during admission, which has established psychometric properties in cancer. The ISI is a 7 item scale which characterizes the type of sleep problem (difficulty falling asleep, staying asleep or waking up too early), and assesses impact (sleep satisfaction, associated distress and impact on others).⁵ The psychometric properties of the ISI in cancer patients are well established, with a cut-off of 8 having optimal sensitivity and specificity.

7.8.5 Inpatient resource utilization:

Variables include duration of admission (days), daily medications, investigations (blood tests, imaging, urine cultures), and level of nursing required for transfers or care (independent, standby assistance, one or two assistants) and use of one to one nursing (hours).

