11.3 Statistical analysis of secondary end points

For the secondary outcomes, time-to-event analysis, such as survival analysis will be used to determine differences in time to first episode of delirium. Delirium precipitants, which occur at variable times and for different durations during the study period are time-dependent covariates and Cox proportional hazard modelling will be used.

The incidence rate of delirium will also be calculated and compared between the treatment and control groups. For possible toxicity of the medication, incidence of adverse event will be calculated and reported.

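### After entry, protocol bloods are taken only at delirium occurrence, so new laboratory precipitants are sought unequally in cases and non-cases, and their Cox hazard ratios can be inflated

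*Protocol*

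**What the plan says.** **Sampling.** Protocol 7.1 states that the blood tests "will be taken to ensure eligibility is met and at delirium occurrence to assess contributing factors to the aetiology of the delirium episode". The table of study measures (8.1) marks liver function, electrolytes and full blood count in the eligibility and delirium-occurrence columns only. The Trial Summary agrees: "15ml blood will be drawn at baseline and any delirium events". Section 13.2.2 lets eligibility use results from the preceding seven days.

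**Analysis.** Section 11.3: "Delirium precipitants, which occur at variable times and for different durations during the study period are time-dependent covariates and Cox proportional hazard modelling" is planned. (The Trial Summary names a proportional logistic model for the same purpose; this point follows 11.3.)

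**Other recording of precipitants.** Section 7.7.1 has participants assessed daily for precipitants. Table 8.1 schedules the Delirium Etiology Checklist at baseline and at delirium. Section 7.8.3 adds "This checklist will also be completed during the study period if new precipitants are identified" and "Day of resolution of prior precipitant will also be recorded", and the checklist draws on all clinical sources.

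**Resource use.** Section 6.2 counts "investigations (blood tests, imaging, urine cultures" among the inpatient resource variables. The economic evaluation under 5.14, repeated in 11.4, includes "resource data (intervention costs, hospital length of stay, health professional time, medication use and investigations". Nothing says that panels required by the protocol are left out.

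**The concern.** A Cox model with a time-dependent covariate compares each case, on the day of the event, with everyone still at risk that day. The comparison is fair only if the covariate is ascertained equally in both. Here the case has a full panel because delirium occurred, while the comparators have whatever ward care ordered. Many checklist items depend on such results, for example uraemia, anaemia, and sodium, potassium or calcium disturbance.

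An abnormality that is merely common would then look like a precipitant. Section 6.2 gives a profile of delirium risk and precipitants as one purpose of the secondary endpoints, so those hazard ratios are likely to be read.

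The lesser issue is that a panel attached to each delirium episode enters the resource and cost totals. Section 7.10 also plans to extrapolate resource use conditional on events, which would carry a trial-only panel forward.

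**Working it through.** The plan gives no figure for this point, so there is none to reproduce.

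**Which abnormalities can be affected.** Everyone has the panel at eligibility and a checklist at baseline, so an abnormality present at entry is known in cases and non-cases alike. Only abnormalities arising after entry are open to outcome-triggered detection.

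**Inputs from the protocol.** N = 220, 110 per arm (11.5); a 21-day period (5.1, 11.5); delirium incidence 20% to 45% (1.1).

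**Assumed inputs, not in the protocol.** The share of days with routine bloods is 10% to 100%. The 21-day probability of a new laboratory abnormality is 30% or 60%. Stay averages about 14 days before the cap at 21. Incidence is applied as a constant daily risk over 21 days, before discharge.

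**Method.** The abnormality has no effect on delirium (true hazard ratio 1). It counts as present from the day it is detected, by a routine test or by the panel on the onset day. A Cox partial likelihood is fitted with one binary time-dependent covariate. Entries are median hazard ratios over 300 replicates.

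| Routine testing, share of days | Incidence 20%, abnormality 30% | 20%, 60% | 45%, 30% | 45%, 60% |
|---|---|---|---|---|
| 10% | 2.65 | 3.18 | 2.64 | 3.24 |
| 20% | 1.73 | 1.93 | 1.59 | 2.01 |
| 33% | 1.24 | 1.47 | 1.30 | 1.47 |
| 50% | 1.18 | 1.21 | 1.15 | 1.16 |
| 100% | 0.92 | 0.96 | 1.05 | 1.00 |

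With the onset-day panel not counted, and testing at 10%, 33% or 100% of days, the twelve values lie between 0.91 and 1.05, that is, around 1 within simulation scatter. The inflation therefore comes from the triggered panel, not from sparse testing as such.

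**Resource count.** Mandated panels per arm = incidence × 110: 0.20 × 110 = 22 and 0.45 × 110 = 49.5, or about 50. The between-arm difference per patient from the mandate alone is the difference in incidence. For assumed incidences of 25% versus 10% it is 0.25 − 0.10 = 0.15 panel; for 45% versus 25% it is 0.45 − 0.25 = 0.20 panel. Both are upper limits, because some panels would have been ordered clinically.

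**The case against.** **Precipitants are assessed daily from all sources, and the checklist is repeated for new ones.** This stands as mitigation. It would be wrong to infer that delirium-free participants have no precipitant data. But the repeat checklist is prompted by a precipitant having been identified, and no text requires comparable testing without delirium. The bias shrinks as ward testing becomes more frequent and does not vanish until testing is close to daily.

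**Exposure coding belongs in the SAP.** Partly right. Section 11.3 does not say that exposure starts on the detection date, and the bias needs onset-day findings to be counted as preceding delirium. However, the protocol fixes both the sampling schedule and the model. A lagging rule is useful only if dated results are collected for everyone; the protocol counts blood tests but does not say that their dated results are extracted.

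**A reader might infer far larger inflation.** Take an abnormality with prevalence p, of which ward care has found a fraction d. The apparent odds ratio at the event is [p/(1−p)] / [dp/(1−dp)]. With p = 0.4 and d = 0.25 this is 0.667/0.111 = 6.0. That does not fit this protocol for abnormalities present at entry: the eligibility panel makes d about 1, and the formula then gives 1.

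**A reader might infer a material distortion of the resource comparison.** The planned contrast is melatonin against placebo, not delirium against no delirium. It is affected only through a difference in incidence, by a fraction of a panel per patient. Nor can every onset panel be called trial-only, since its stated purpose is to find the cause of the episode; removing clinically ordered panels would understate the cost of delirium.

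**Conclusion.** The concern holds in limited form. For laboratory-defined precipitants arising after entry, ascertainment is triggered by the outcome, and the planned Cox model can give inflated hazard ratios. With onset-day findings counted as exposure, the spurious hazard ratio is about 2.6-3.2 with routine testing on one day in ten, 1.6-2.0 on one in five, 1.2-1.5 on one in three, and about 1.0 with daily testing. These sizes rest on assumed testing frequencies and abnormality rates; the direction does not.

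The primary outcome and the unadjusted randomised comparison of time to delirium are unaffected, as are precipitants that need no blood test, such as drug withdrawal. The resource-use effect is minor: at most one panel per episode, and 0.15 to 0.20 panel per patient between arms in the examples. The change is worth making because it is cheap and removes a bias that the stated schedule and model create together.

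**What to change.** **Sections 7.1 and 11.3.** Define laboratory precipitants from dated results extracted in the same way for all participants. Count as exposure only results dated before the day of delirium onset, with the same lag applied to everyone at risk on that day. Use the delirium-triggered panel only to describe the episode.

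**Sections 6.2, 7.8.5 and 11.4.** Flag panels taken solely because the protocol requires them and exclude them from resource counts and costs. Keep those ordered clinically.

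**Cost.** A change of wording, extraction of dated routine pathology results for all participants, and one flag on the case report form. No extra blood sampling is needed. The downside is that true precipitants first detected on the onset day are not counted, so real effects may be somewhat attenuated and fewer precipitants can be dated.
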